Once parents completed the informed consent which confirmed their participation in the study and income proxy screener (i.e., public assistance services utilized and parent education), children were randomly allocated at a 1:1 ratio to either control (i.e., summer as usual) or intervention (i.e., free SDC), stratified by public assistance services used/received within family units, grade, and gender. Where parents had two or more eligible children, siblings were grouped together to ensure siblings were randomized to the same condition. Children were allowed to participate in the study for a single summer. Randomization occurred prior to baseline assessments each May. The decision to randomize at this time was made to treat the participating families with dignity and be respectful of their needs in making alternative summer care arrangements if their child was not randomized to receive free SDC. Randomization was performed by a co-investigator ([name]) external to the day-to-day conduct of the trial using a stratified random number generator in STATA (StataCorp LLC, v.18.0). The lead investigator ([name]) and data collectors were blinded to allocation.

Intervention and Control Conditions.

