Sample size calculations were based on the ability to detect a statistically significant group (intervention vs control) by time (before summer to end of summer) difference in the change in zBMI with a mixed-effects model with statistical power of 0.80 and an alpha of 0.05. Estimates from the largest and most recent studies¹⁵⁻¹⁷ conducted to date reported the average change in zBMI during the summer ranged from 0.04 to 0.09, and the average change in zBMI during the school year was -0.02. Accounting for the intraclass correlation at the school level¹⁸ and an anticipated attrition rate of 25%, the total number of children required to be enrolled at baseline was 420 to arrive at a final sample of 330 (165 per condition).

Statistical Analyses.

BMI. The primary analysis was intent-to-treat (ITT), defined as using all available data from children according to the original group they were randomized (free summer day camp or continue summer as usual) regardless of their attendance at a summer program. Analyses used mixed-effects models, accounting for the nesting of repeated measures within children, families (i.e., siblings), and schools. The treatment effect of interest was the group (intervention vs control) and time (pre summer vs post summer) interaction. Missing data on the primary outcome (zBMI) was accounted for using full information maximum likelihood estimation, allowing for all children's zBMI data to be used regardless of missing zBMI at either pre or post summer. Covariates included in

the model were the child's baseline zBMI, biological sex¹⁹ and age,²⁰ self-reported race/ethnicity,²¹ parent education,²² food insecurity status,²³ and poverty level.²⁴ Missing data on covariates were handled using multivariate multiple imputation of 100 datasets for both continuous and categorical covariates using STATA v18.0 multiple imputation commands. Secondary analyses examined the dose-response of summer program attendance including both the intervention and control groups. These models used each of the three summer program exposure metrics as continuous independent variables (standardized to the percentage of days attended during the week), to examine the impact of the amount of summer programming on changes in zBMI. The assumptions for all models were checked using plots of the estimated residuals, no violations were found.

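### The primary zBMI model names a family level but not its form; read as random intercepts, it gives the group-by-time test almost no protection for siblings randomised together

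*Combined protocol and SAP*

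**What the plan says.** Randomization and Blinding: where a parent enrolled more than one child, "siblings were grouped together to ensure siblings were randomized to the same condition". For families with several children in the trial, the thing randomised is therefore the family.

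Statistical Analyses, BMI: "Analyses used mixed-effects models, accounting for the nesting of repeated measures within children, families (i.e., siblings), and schools". The same paragraph defines the primary test: "The treatment effect of interest was the group (intervention vs control) and time (pre summer vs post summer) interaction". There are two zBMI measurements per child, and children with only one are kept through full information maximum likelihood.

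Statistical Power: the only clustering mentioned is at school level ("Accounting for the intraclass correlation at the school level"). No family or sibling correlation appears.

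The documents do not say whether the family level is an intercept alone or also has a time slope. They do not give the residual structure, or say whether standard errors are model-based or cluster-robust. The number of sibling sets is not reported.

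**The concern.** Listing families among the levels looks like an adjustment for joint allocation. Whether it is one depends on the form of the term. A random intercept describes how similar siblings are in zBMI level. The primary test concerns change over one summer, and what matters for its standard error is how similar siblings are in change. Siblings share a household and an allocation, and each summer offered a single camp, so some positive correlation of change is plausible. If the model has no term for it, the test treats every child's change as independent although siblings were randomised as one unit.

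At stake are the confidence interval and p-value of the primary outcome. The plan cites small changes ("the average change in zBMI during the summer ranged from 0.04 to 0.09, and the average change in zBMI during the school year was -0.02"), so even a modest error in the standard error could decide whether the result is called significant.

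**Working it through.** **The plan's own figures.** The plan aims for a test "with a mixed-effects model with statistical power of 0.80 and an alpha of 0.05", with 420 enrolled and 330 analysed. The 330 cannot be rebuilt, because the target difference, the SD of change and the school correlation are not given. The enrolment step does not reproduce either: 330 / (1 − 0.25) = 440, and 420 × 0.75 = 315. That is a separate matter and does not affect what follows.

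**Step 1: what an intercept does to the interaction.** For child i in family j at time t, with random intercepts only (the school intercept behaves in the same way):

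y = fixed part + f(j) + c(ij) + e(ijt)

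August minus May for the same child:

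change = time effect + (group × time effect) × arm + e(ij, August) − e(ij, May)

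Both f(j) and c(ij) are gone. The model takes the remaining errors as independent between siblings, so its standard error is that of a two-sample comparison of changes.

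**Step 2: numerical check.** Exact generalised least squares with 420 children and an assumed SD of change of 0.25, school level left out:

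- Complete data: 0.25 × √(1/210 + 1/210) = 0.0244. The model gives 0.02440 with the family intercept and 0.02440 without it.
- 25% of children missing one measure: 0.0279 with and 0.0279 without.

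**Step 3: size of the understatement.** Let s be the share of children with a sibling in the trial, m the size of a sibling set, and ρ the correlation between siblings' changes in zBMI. All three are assumptions. With complete data:

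- Design effect DE = 1 + s(m − 1)ρ
- True SE / model SE = √DE
- Actual two-sided type I error = 2[1 − Φ(1.96/√DE)]

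Example with pairs (m = 2), s = 0.59, ρ = 0.6: DE = 1 + 0.59 × 0.6 = 1.354; √DE = 1.164; 1.96/1.164 = 1.684; type I error = 9.2%.

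SE ratio and type I error for pairs:

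| ρ | s = 27% | s = 41% | s = 59% |
|---|---|---|---|
| 0 | 1.000; 5.0% | 1.000; 5.0% | 1.000; 5.0% |
| 0.1 | 1.013; 5.3% | 1.020; 5.5% | 1.029; 5.7% |
| 0.4 | 1.053; 6.3% | 1.079; 6.9% | 1.112; 7.8% |
| 0.6 | 1.078; 6.9% | 1.116; 7.9% | 1.164; 9.2% |

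Sets of three raise the figures: with s = 0.5 and ρ = 0.3, DE = 1 + 0.5 × 2 × 0.3 = 1.30, the ratio is 1.140 and type I error 8.6%.

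**Step 4: missing measures.** In the model of step 2, with half the children in pairs and ρ = 0.3, the ratio falls from 1.072 on complete data to 1.056 when 25% of children lack one measure. The problem shrinks a little but remains.

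**The case against.** The strongest reply is that the plan does name families, and nothing in it says that the level is an intercept only. Its wording is also compatible with a family-by-time term or with cluster-robust standard errors. That stands. A reader might infer that joint allocation was ignored and that the primary standard error is wrong. The documents do not support this: they leave the specification open, and they contain no primary interval that could be shown to be wrong.

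Second, the understatement needs a positive sibling correlation of change. Correlation in zBMI level is not the same thing, and a difference over about three months carries measurement error that siblings do not share. This also stands. At ρ = 0 there is no inflation, and at ρ = 0.1 it is under one percentage point, so a flat statement that type I error exceeds 0.05 goes too far.

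Third, the planned model has more in it than the algebra above: baseline zBMI as a covariate, a school level, and children with one measure. With the baseline covariate the exact match to a two-sample test is lost, but protection is not gained. In a simulation with half the children in pairs and ρ = 0.5, the model SE was 0.0260 against an empirical SD of 0.0311. Part of that gap comes from the covariate itself, since the two-sample SE was 0.0275. With 30% in pairs and ρ = 0.3, type I error was 5.3% in 600 runs, which cannot be told apart from 5%.

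**Conclusion.** The point holds conditionally. The family is the unit of randomisation, and the stated nesting, in its ordinary reading, does not carry that into the primary interaction test. The primary standard error is too small if two things are both true: the family level was fitted without a time component and without family-clustered errors, and siblings' summer changes are positively correlated. Neither is documented.

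Under the assumed ranges (pairs, 27% to 59% of children with a sibling in the trial, correlation 0 to 0.6) the true standard error exceeds the model's by 0% to about 16%, and type I error runs from 5.0% to about 9%. The cancellation is certain for an intercept; the size of its consequence is not. On either reading the plan lacks the detail a reader needs to judge whether the primary interval respects the randomisation.

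**What to change.** In Statistical Analyses, BMI:

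- State that the family is the unit of randomisation.
- For the primary group-by-time test, specify either a family-by-time random effect (a family random slope on time), or standard errors clustered on family with school entered as fixed effects. School then no longer sits as a random level above the cluster.
- Keep every child with either measure. Analysing one row per child, August on May zBMI, is not preferred: it drops children with only one measure, against the plan's stated use of all available data.
- Report the number and size of sibling sets.
- If the fitted model had intercepts only, re-run it and report the corrected interval. If it already held such a term or clustered errors, say so.

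Cost: one model term or option, one re-run, and a slightly wider interval. In the 420-child calculation on complete data, the SE with a correctly specified family-by-time term was 0.02474 against 0.02440 (1.4% wider) with 30% of children in pairs and ρ = 0.1, and 0.02673 against 0.02440 (9.5% wider) with 50% in pairs and ρ = 0.5.

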MVPA, Screen Time, Sleep. The primary analysis was intent-to-treat (ITT), defined as using all available data from children according to the original group they were randomized (free summer day camp or summer as usual) regardless of their attendance at a summer program (e.g., intervention children never attending the SDC and control children attending some other form of SDC). Analyses used mixed-effects models, accounting for the nesting of repeated measures within children, families, and schools. The treatment effect of interest was the group (intervention vs control) and time (pre summer vs post summer) interaction. Missing data on the dependent variables of interest of MVPA, time spent sedentary, sleep, and screen time were accounted for using full information maximum likelihood estimation,²⁵ allowing for all children's data to be used regardless of missing data at either pre or post summer. Covariates included in the model were the child's biological sex¹⁹ and age,²⁰ self-reported race/ethnicity,²¹ parent education,²² food insecurity status,²³ and poverty level.²⁴ Missing data on covariates were handled using multivariate multiple imputation with the covariates serving as variables to inform the imputation of 100 datasets for both continuous and categorical covariates using STATA v18.0 multiple imputation commands.

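### As the zBMI model is naturally read, its covariates do not act on change: the ITT effect is in practice unadjusted, and listing baseline zBMI beside pre-summer zBMI understates the standard error

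*Combined protocol and SAP*

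**What the plan says.** Statistical Analyses, BMI, describes one mixed model for two measurements per child: "Analyses used mixed-effects models, accounting for the nesting of repeated measures within children, families (i.e., siblings), and schools". The effect is defined as follows: "The treatment effect of interest was the group (intervention vs control) and time (pre summer vs post summer) interaction". The covariate list begins with baseline zBMI ("the model were the child's baseline zBMI, biological sex") and continues with age, race/ethnicity, parent education, food insecurity and poverty level. Each has one value per child. The section does not say whether any of them interacts with time.

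Missing zBMI is handled by full information maximum likelihood, "allowing for all children's zBMI data to be used regardless of missing zBMI at either pre or post summer". Statistical Power anticipates 25% attrition.

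For the secondary analyses, "Secondary analyses examined the dose-response of summer program attendance including both the intervention and control groups". The three exposure metrics enter as continuous variables "to examine the impact of the amount of summer programming on changes in zBMI". The section does not say whether that means an exposure-by-time term or a regression of change, nor whether the covariate list carries over.

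The MVPA, Screen Time, Sleep section has the same group-by-time structure ("Covariates included in the model were the child's biological sex", and so on), without the baseline outcome. The Diet section differs: it models the summer outcome controlling for the school-year value.

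**The concern.** The covariates are presumably there to sharpen the ITT comparison, to correct chance imbalance and to support the likelihood handling of missing August values. In the dose-response models, if they are used there, they would also control confounding. In a two-time-point model whose tested term is a change, a child-constant main effect does none of this for the change. A reader would take the results as covariate-adjusted when the tested coefficient is essentially the crude one.

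The dose-response models have most at stake. They pool both arms, and the Summer Programming Exposure section recognizes that families in either arm may choose whether to attend, so randomization does not protect the slope.

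Baseline zBMI raises a different problem. Pre-summer zBMI then stands on both sides of the equation, which affects the standard error and not only the adjustment.

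**Working it through.** **Inputs from the documents.** Two time points; group-by-time effect; alpha 0.05 (two-sided assumed); 25% attrition; 420 enrolled; cited summer zBMI changes of 0.04 to 0.09. **Assumed, because the documents do not give them:** SD of change 0.25 or 0.30, and the covariate, confounder and dropout strengths below. Family and school levels are left out of the calculations. The plan states no figure that this point could reproduce.

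**1. Covariates cancel.** With main effects only, for child *i* with arm A and covariates C,

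Y(pre) = a + bA + gC + u + e₀ and Y(post) = a + d + (b + θ)A + gC + u + e₁.

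Subtracting gives Y(post) − Y(pre) = d + θA + (e₁ − e₀). Both gC and u vanish. The same holds with an exposure metric in place of A.

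Simulation (420 children, SD of change about 0.30) agrees. With complete pairs, the interaction with and without covariates differs by about 10⁻¹⁵. With 25% of August values missing, the mean absolute shift is 0.0005 to 0.0018 for ITT against a standard error of about 0.035, and 0.0009 to 0.0028 for dose-by-time against about 0.056.

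**2. ITT precision.** If covariates explain a share R² of the variance of change, the unadjusted standard error is 1/√(1 − R²) times the adjusted one: 1.026, 1.054 and 1.118 for R² of 5, 10 and 20%. In the simulation the empirical SD fell from 0.0281 to 0.0274 (2.5%) with covariate-by-time terms, and the mean estimate barely moved (−0.0505 to −0.0502).

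**3. ITT bias from dropout.** If dropout depends on a covariate equally in both arms, the arms keep the same covariate mix and the difference in change is not biased. Suppose instead that a binary covariate (prevalence 50%) moves change by 0.10, that August is missing for 40% versus 10% by that covariate in control, and for 25% throughout intervention. Among control children with August data, the covariate share is 0.5 × 0.6 / (0.5 × 0.6 + 0.5 × 0.9) = 0.40, against 0.50 in intervention. The bias is 0.10 × (0.50 − 0.40) = 0.010. Simulations gave 0.008 to 0.010, and about zero with covariate-by-time terms. Against a sampling SD of 0.032 this is about 0.25 to 0.31 SE, which lifts a 5% test to about 6%.

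**4. Dose-response, if exposure-by-time with main-effect covariates.** Let the true slope be zero and the confounder correlate r₁ with attendance and r₂ with change. The induced correlation is r₁r₂. With n = 420 × 0.75 = 315, the expected z is about r₁r₂√315:

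| r₁, r₂ | r₁r₂ | z | False positives |
|---|---|---|---|
| 0.1, 0.1 | 0.01 | 0.18 | 5.4% |
| 0.2, 0.1 | 0.02 | 0.35 | 6.5% |
| 0.2, 0.2 | 0.04 | 0.71 | 11% |
| 0.3, 0.2 | 0.06 | 1.06 | 19% |
| 0.4, 0.3 | 0.12 | 2.13 | 57% |

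Simulation at (0.3, 0.2) gave 17.6% with no covariates, 17.7% with main effects, and about 4% when the covariates act on change.

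**5. Baseline zBMI as covariate and outcome.** Given baseline, the pre-summer rows are fitted exactly (crossed with time) or almost exactly (main effect), and the child variance is estimated as zero. The residual variance is then pooled over N near-zero pre-summer residuals and 0.75N August residuals: σ² × 0.75/1.75 = 0.4286σ², where σ² is the variance of change. With n children per arm, the model variance of the interaction is 0.4286σ² × (2/n) × (1 + 1/0.75) = σ² × 2/n. That is the variance with nobody lost. The correct value is σ² × 2/(0.75n). The SE ratio is √0.75 = 0.866, and the false-positive rate is 2Φ(−1.96 × 0.866) = 9.0%.

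Simulation agrees: model SE 0.0296 against empirical SD 0.0342 (ratio 0.866), and 8 to 10% ITT false positives whether baseline enters as a main effect or crossed with time. Regressing August zBMI on arm, baseline and covariates gave 4.9%. With no missing data the two variances coincide and the problem disappears.

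**The case against.** The strongest reply is that the plan never says main effects only. That is correct: the text is silent, and main effects are the natural reading because the one interaction of interest is spelled out and no other is. If covariate-by-time terms were fitted, steps 1 to 4 fall away and only the reporting gap and step 5 remain.

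A reader might infer that the ITT estimate is biased. The documents do not support this. The arms are randomized, with stratification by public assistance, grade and gender, so an unadjusted contrast is valid. The dropout scenario in step 3 needs a covariate effect larger than the whole cited summer change and an arm-specific missingness pattern that nothing in the documents indicates.

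A reader might also infer that the dose-response slope has no confounder control. That goes too far. A within-child contrast already removes stable differences in zBMI level, and the wording also fits a regression of change, in which the same covariates would adjust properly. In simulation with a true slope of −0.05, that regression gave −0.049 to −0.051, while exposure-by-time with main effects gave about −0.14. What stands is that the plan does not say which was used.

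Finally, the MVPA, sedentary, sleep and screen-time outcomes rest on 14-day assessments with possibly unequal numbers of days per child. The cancellation was not checked for such data, so only the structural argument carries over.

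**Conclusion.** The point holds under the natural reading of the model. For the ITT analysis, the inert covariates cost a little precision (about 2% in simulation; more if covariates explain much of the change) and leave chance imbalance uncorrected. Bias arises only with covariate-related dropout that differs by arm.

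The more concrete ITT problem is baseline zBMI on both sides of the model. At the plan's own 25% attrition, the standard error is about 13% too small and the nominal 5% test runs at roughly 8–10%. This assumes that the losses are August values, that the model is a random-intercept model with a common residual variance, and that the family and school levels do not change the picture.

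The matter weighs most on the dose-response analysis, where confounding of change is a real possibility and neither form nor adjustment set is stated. The false-positive figures there show direction and sensitivity only, because they follow directly from the assumed correlations. Overall this should be fixed for the ITT analysis and matters most for the dose-response models.

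**What to change.** State the model equation. For the primary zBMI analysis use one of two forms:

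- regress August zBMI on arm, baseline zBMI and the listed covariates, with family and school random effects; or
- keep both time points as outcomes, remove baseline zBMI from the covariates, and cross the remaining covariates with time.

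Crossing baseline zBMI with time while pre-summer zBMI stays an outcome should be avoided, since it keeps the standard-error fault of step 5.

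Use the chosen form for all three dose-response models and list their covariates. Add covariate-by-time terms to the group-by-time models for MVPA, sedentary time, sleep and screen time.

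The cost is SAP wording, a re-run on data already collected and a few degrees of freedom. The first form does not use children without an August measurement and needs imputation where baseline is missing. The second keeps children with either measurement.

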The intervention group was randomly assigned to receive 8 to 10 weeks of free SDC. The difference in the number of weeks was due to summer 2021 being shorter than summers 2022 and 2023 because of COVID-19 school closures. The SDC that served as the intervention was operated by a local parks and recreation commission, which operated multiple summer programs across the school district. The SDC provided indoor and outdoor opportunities for children to be physically active each day, included enrichment and academic programming, weekly field trips, and provided breakfast, lunch, and snacks. The foods served adhered to existing federal food program nutrition guidelines by the USDA and were reimbursed via the Summer Food Service Program (<https://www.fns.usda.gov/summer/sunmeals>). The SDC maintained a ratio of 1 staff member for every 12 children enrolled – consistent with childcare regulations. The SDC operated daily (Mon-Fri) for 8 to 10 weeks during the summer (except for the 4th of July holiday week). The SDC opened at 7am for morning drop-off and ended at 5pm each day. Based on the schedules of the SDC, physical activity opportunities were scheduled for 3 to 4 hours each day, with the remaining 4 to 5 hours dedicated to enrichment/academic content or field trips. An example menu and daily schedule are provided in Supplemental eFigure 1. The local parks and recreation commission had a history of operating SDCs in the community and had the appropriate safety and staff training certifications to ensure a safe/nurturing environment. Each summer a single SDC was provided for children to attend. The SDCs operated according to routine practice, with no outside assistance or modifications from the investigative team. In summer 2022 and 2023, the school district provided transportation for children assigned to the intervention group. No transportation was provided in 2021 due to COVID-19. The control group did not receive free SDC programming. These children experienced what we consider “summer as usual” (see Summer Programming Exposure below).

Measures

BMI z-score.

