Secondary analyses (i.e., exposure models) examined the exposure to structured programming and included both the intervention and control groups. For these analyses we defined exposure to structure as any day where a child is reported on the TUR to have attended a structured setting outside the home (attended/not attend, binary variable). This choice of dichotomizing structured settings at the day level was done because the distribution of minutes in a structured setting was heavily skewed in the summer. Children (both intervention and control), when they were reported to have attended a structured setting in the summer, did so for a day-long program (i.e., 7-8hrs), which for the intervention group was the typical length of attending the SDC. This means that for the children in the control group, when they did attend structured programming in the summer, this programming lasted for approximately the same length of time as the intervention group. Because all children were exposed to school, exposure to structured programming during school (April/May) excluded attending school and, therefore, represents only additional structured programming a child was exposed to above and beyond the school day. In addition to changes in the continuous outcomes, we examined the probability of meeting MVPA (≥ 60 minutes per day) and screen time (≤ 120 minutes per day) guidelines²⁶ using both the above stated ITT and exposure to structured programming models. All models included both weekdays and weekend days. Because free SDC was provided on weekdays only, we also conducted the same ITT and exposure analysis restricting the data to only weekdays. The assumptions for all models (normality of residuals, homoscedasticity) were checked using; no violations were found. All models were conducted using STATA v18.0 (College Station, Texas).

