Diet. The primary analysis was intent-to-treat (ITT), defined as using all available data from children according to the original group they were randomized to (free SDC or summer as usual) regardless of their parent-reported attendance at a summer program.²⁷ Mixed effects models were used to account for the nesting of repeated daily measures within children. The analyses examined the odds of consuming different foods/beverages during weekdays in the summer, controlling for school year endorsement of consuming that food or beverage, in the free SDC group compared to summer as usual. During analysis, day-level food/beverage response options (e.g., 1 time today, 2-3 times today) were collapsed and recoded as binary values: 1 = consumed and 0 = did not consume. Analyses excluded weekend days as the intervention was only delivered on weekdays. Missing data for outcome variables were accounted for using full information maximum likelihood estimation, allowing for all children's data to be used regardless of missing data. Covariates included child biological sex, parent education, food security status, the use of assistance services (e.g., SNAP, WIC), and income. Missing data for covariates was handled using multiple imputation of 100 datasets for both continuous and categorical covariates.

Secondary analyses were as-treated, defined as using all available data from children based on their parent-reported attendance at a structured program on weekdays in the summer, regardless of what group they were randomly assigned to.²⁸ This analysis examined the impact of attending structured summer programming, both

as a binary predictor (days children attended vs days not attended) and as categorical minutes attended (30-239min/d or ≥ 240 min/d vs did not attend “zero” minutes [reference group]) on the odds of consuming different food/beverages during weekdays in the summer, controlling for consumption during the school year and all covariates included in the primary analysis. The 30-239min/d grouping corresponds to half-day or shorter programs, while ≥ 240 min/d corresponds to longer than half-day up to full-day programs. The assumptions for all models were evaluated by examining multicollinearity, residual plots, and the distribution of random effects; no violations were found. STATAv17.0 was used to run all statistical analyses

References

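### The attendance-based zBMI and diet models are observational and should not be called impact; the all-days activity exposure models also need a weekend term

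*Combined protocol and SAP*

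**What the plan says.** All references are to the combined protocol and SAP.

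- **Summer Programming Exposure.** Control families may enrol in other programmes (about 20% expected), and intervention families may decline the free camp or use another programme. Exposure is measured three ways: a June survey of planned enrolment, a weekly attendance survey, and a 14-day July time-use record of which only weekday records are used.
- **Statistical Analyses, BMI.** The primary analysis is intention-to-treat. Secondary models put each of the three metrics in as a continuous predictor, with both arms included, "to examine the impact of the amount of summer programming on changes in zBMI".
- **Statistical Analyses, Diet.** The secondary analysis is as-treated and disregards assigned group: "This analysis examined the impact of attending structured summer programming". It adjusts for school-year consumption and the primary covariates, and excludes weekends.
- **Statistical Analyses, MVPA, Screen Time, Sleep.** The secondary exposure models count a day as exposed if the time-use record shows any structured setting away from home. "All models included both weekdays and weekend days". A weekday-only rerun of the same models is also described.
- **Intervention and Control Conditions.** "The SDC operated daily (Mon-Fri) for 8 to 10 weeks during the summer".

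No instrument, complier-type estimate, weekend term, within/between-child split or statement that the attendance results are associational is given.

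**The concern.** Randomisation protects the comparison of assigned groups. It does not protect a comparison of children who attended more with children who attended less. Families who use a programme regularly may differ in work pattern, transport, health or household routine, and measured covariates remove only the part of this that they capture. For the zBMI dose-response and activity exposure models even that adjustment is implied rather than stated. The June metric is the most exposed of the three, because it records what families planned rather than what children did.

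The activity models have a second problem. If exposed days fall almost wholly on weekdays and unexposed days include most weekend days, a single attended/not-attended term takes up any ordinary weekday-weekend difference.

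At stake is whether an attendance coefficient may be read as what the programme does.

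**Working it through.** **1. The plan's own figure.** The only computed figure is the primary sample size: "with a mixed-effects model with statistical power of 0.80 and an alpha of 0.05", with the total "enrolled at baseline was 420 to arrive at a final sample of 330 (165 per condition"). The target difference, SD and intraclass correlation value are not stated, so 330 cannot be rebuilt. Inverting the two-sample formula (two-sided alpha assumed, clustering ignored):

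- d = (1.960 + 0.842) × √(2/165) = 0.308 SD.
- As a correlation, r = d/√(d² + 4) = 0.308/2.024 = 0.152.
- The background figures are that "the average change in zBMI during the summer ranged from 0.04 to 0.09, and the average change in zBMI during the school year was -0.02". Differences of 0.04 to 0.11 (0.09 + 0.02) would imply a change SD of 0.04/0.308 = 0.13 to 0.11/0.308 = 0.36.

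On attrition, 330/0.75 = 440 and 420 × 0.75 = 315, so 420, 330 and 25% do not agree exactly. That is a separate matter, and nothing below depends on it.

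**2. Self-selection, closed form.** Suppose an unmeasured family factor has the same correlation ρ with attendance and with zBMI change, and the programme has no effect. The spurious correlation is ρ². The values of ρ are assumptions.

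| ρ | spurious r | share of 0.152 |
|---|---|---|
| 0.1 | 0.01 | 7% |
| 0.2 | 0.04 | 26% |
| 0.3 | 0.09 | 59% |

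**3. Self-selection, simulation under no effect.** There were 330 children and 4,000 replicates. Assumed, not from the documents: change SD 0.3, 60-95% of intervention children attending, correlation of the factor with change 0.1-0.3, and its loading on attendance 0.3-0.5.

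| Model | False-positive rate (nominal 0.05) |
|---|---|
| Intention-to-treat | 0.05-0.06 |
| Pooled dose model | 0.06-0.44 |
| Dose model plus arm | 0.06-0.49 |
| Assignment as instrument | 0.04-0.06 |

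The false dose slope ran from -0.007 to -0.079 zBMI between 0% and 100% attendance. The instrumental estimate had bias of 0.003 or less. When the factor was unrelated to change, the dose model's rate was 0.05-0.06.

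**4. Weekend days, closed form.** Take 14 days (10 weekdays, 4 weekend days), weekday attendance a, and a fraction q of weekend days exposed. The false contrast equals the weekday-weekend gap × (weekend share of unexposed days − weekend share of exposed days). With q = 0 the first share is 4/(4 + 10(1 − a)) and the second is 0. For an assumed 10-minute gap:

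| q | a = 0.2 | a = 0.8 |
|---|---|---|
| 0 | 3.3 min | 6.7 min |
| 0.1 | 1.4 min | 6.0 min |
| 0.2 | 0 min | 5.2 min |

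Example for q = 0.1, a = 0.8: 3.6/5.6 − 0.4/8.4 = 0.643 − 0.048 = 0.595, times 10 = 6.0.

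**5. Which contrast is reported.** This was simulated for MVPA with no programme effect (150 replicates) and an assumed 5-minute summer gap.

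- Summer-only contrast, no weekend exposure: about 3.4-3.6 min, rejection 0.88-0.93.
- Exposure-by-period term, same gap in both periods: 0.5-0.7 min (rejection 0.07-0.11); with 10% weekend exposure, 1.3-1.6 min (0.13-0.22).
- Exposure-by-period term, gap in summer only and no weekend exposure: 2.5 min (0.30).
- Weekday-only model, or weekend-by-period term added (summer gaps of 3-5 min): within about 0.35 min of zero, rejection 0.03-0.07, which is nominal within simulation error.

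**The case against.** The best defence is that the plan already ranks these analyses. Intention-to-treat is primary for every outcome, the attendance models are secondary, and the diet model is openly called as-treated and adjusts for baseline consumption. The activity section speaks of exposure, not impact. Part of the variation in attendance comes from randomisation itself, which dilutes the selection bias. At the mild end of the assumptions the dose model is close to nominal. An instrumental-variable estimate also answers a different question from a dose-response across all programmes. All of this stands, and it limits the point to interpretation of secondary results. It does not justify *impact* for the zBMI and diet estimates.

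On weekends, a reader might infer that every weekend day is coded as unexposed. The documents do not say so: a structured setting on any recorded day counts, so a weekend day can be exposed. That most would not be follows from the camp's weekday schedule and from the plan's own treatment of weekdays as the days when programmes could be attended. A reader might also suppose that the issue was overlooked, but the weekday-only exposure run is already described, and the diet analysis drops weekends. The shares of weekend days become bias only if behaviour differs between weekdays and weekends, and the documents give no such gap.

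**Conclusion.** The point holds in a limited form. The zBMI dose-response and diet as-treated estimates are observational, and the word *impact* claims more than they can support. Under assumed confounding the zBMI false-positive rate lies anywhere from near nominal (0.06) to 0.44. The documents do not allow a narrower statement, and no size was derived for diet. The all-days activity exposure contrast can be shifted by an ordinary weekday-weekend difference. The shift is smaller for the exposure-by-period term than for a summer-only contrast, its sign follows the sign of the gap, and the weekday-only run does not have it. That run does not cure self-selection.

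It would be tempting to conclude that the trial's main findings are compromised, or that these models are meant to carry the efficacy claim if intention-to-treat is diluted. Neither follows: the primary analyses do not use attendance, and nothing in the documents assigns the secondary models that role.

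**What to change.** 1. **zBMI and diet.** Keep the attendance models, label them associations and drop *impact*. For zBMI, add a two-stage least squares estimate with randomised group as the instrument for percent of weekdays attended, the same covariates and family-clustered standard errors. Use a metric of reported attendance, not the June plans. State that it assumes assignment acts only through attendance, that its intervals are wider, and that it estimates the effect for children whose attendance the offer changed.
2. **Activity, screen time and sleep.** Make the existing weekday-only exposure analysis the lead one, or add weekend and weekend-by-period terms to the all-days model. Say which contrast is reported.
3. **Optional.** In the day-level models, split attendance into the child's mean and the day's deviation from it, and report the within-child effect. This removes stable family differences but not day-to-day reasons for absence.

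The cost is some further analysis of data already held, plus rewording. Because the document describes completed analyses, anything added should be marked as post hoc.
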